## LIST OF ABBREVIATIONS

AE	adverse event
AED	antiepileptic drug
ALT	alanine aminotransferase
AST	aspartate aminotransferase
ANCOVA	analysis of covariance
bid	twice daily
BMI	body mass index
BP	blood pressure
BRIEF ®	Behavior Rating Inventory of Executive Function ®
BRIEF ® -P	Behavior Rating Inventory of Executive Function ® - Preschool Version
CBCL	Child Behavior Checklist
CI	confidence interval
CSR	Clinical Study Report
C-SSRS	Columbia-Suicide Severity Rating Scale
CTStat	Clinical Trial Biostatistician
CV	coefficient of variation
DAP	Data Analysis Plan
DBP	diastolic blood pressure
DEM	Data Evaluation Meeting
ECG	electrocardiogram
eCRF	electronic Case Report form
ETV	Early Termination Visit
FAS	Full Analysis Set
HRQoL	health-related quality of life
IDMC	Independent Data Monitoring Committee
IVRS	Interactive Voice Response System
LCM	lacosamide
LSM	least squares mean
MA	markedly abnormal
MedDRA ®	Medical Dictionary for Regulatory Activities

---

PBO	placebo
PD	pharmacodynamic
PedsQL	Pediatric Quality of Life Inventory
PK	pharmacokinetic
PK-PPS	Pharmacokinetic Per Protocol Set
PPS	Per Protocol Set
PT	preferred term
SBP	systolic blood pressure
SAE	serious adverse event
SAP	Statistical Analysis Plan
SD	standard deviation
SOC	system organ class
SPD	Specification of Protocol Deviations
SS	Safety Set
TEAE	treatment-emergent adverse event
TEMA	treatment-emergent markedly abnormal
VNS	vagus nerve stimulation
WHODD	World Health Organization Drug Dictionary

## 1 INTRODUCTION

This Statistical Analysis Plan (SAP) defines the scope of statistical analyses and provides a detailed description of statistical methodology for the statistical analyses to support the final clinical study report for SP0969.

## 2 PROTOCOL SUMMARY

### 2.1 Study objectives

#### 2.1.1 Primary objective

- To evaluate the efficacy of lacosamide (LCM) administered concomitantly with 1 to  $\leq 3$  antiepileptic drugs (AEDs) in subjects with epilepsy  $\geq 4$  years to  $< 17$  years of age who currently have uncontrolled partial-onset seizures

#### 2.1.2 Secondary objective

- To evaluate the safety and tolerability of LCM in subjects  $\geq 4$  years to  $< 17$  years of age

#### 2.1.3 Other objective

- To evaluate the pharmacokinetics (PK) of LCM in subjects  $\geq 4$  years to  $< 17$  years of age

### 2.2 Study variables

#### 2.2.1 Efficacy variables

The assessment of efficacy is based on partial-onset seizure frequency.

##### 2.2.1.1 Primary efficacy variable

The primary efficacy variable is:

- Change in partial-onset seizure frequency per 28 days from Baseline to the Maintenance Period

##### 2.2.1.2 Secondary efficacy variables

The secondary efficacy variables include the following:

- Proportion of responders, where a responder is a subject experiencing a 50% or greater reduction in partial-onset seizure frequency from Baseline to the Maintenance Period
- Proportion of subjects experiencing a  $\geq 25\%$  to  $< 50\%$ , 50% to 75%, or  $> 75\%$  reduction in partial-onset seizure frequency from Baseline to the end of Maintenance Period
- Change in partial-onset seizure frequency per 28 days from Baseline to the entire treatment (ie, Titration+Maintenance Periods)
- Proportion of subjects experiencing a  $\geq 25\%$  to  $< 50\%$ , 50% to 75%, or  $> 75\%$  reduction in partial-onset seizure frequency from Baseline to the entire treatment (ie, Titration+Maintenance Periods)
- Proportion of subjects experiencing no change in partial-onset seizure frequency (between  $< 25\%$  reduction and  $< 25\%$  increase) from Baseline to the entire treatment (ie, Titration+Maintenance Periods)

- Proportion of subjects experiencing an increase in partial-onset seizure frequency of  $\geq 25\%$  from Baseline to the entire treatment (ie, Titration+Maintenance Periods)
- Change in partial-onset seizure frequency per 28 days from Baseline to the entire treatment (ie, Titration+Maintenance Periods) by seizure type
- Proportion of seizure-free days during the Maintenance Period for subjects who entered the Maintenance Period
- Proportion of subjects who achieved “seizure-free” status (yes/no) for subjects who completed the Maintenance Period

### **2.2.1.3 Other efficacy variables**

Other efficacy variables to be examined include:

- Clinical Global Impression of Change at the end of the Maintenance Period
- Caregiver’s Global Impression of Change at the end of the Maintenance Period
- Quality of life assessments (PedsQL)
- Health care resource use (concomitant AEDs, medical procedures, health care provider consultations including hospitalizations not foreseen by the protocol)

### **2.2.2 Safety variables**

#### **2.2.2.1 Primary safety variables**

Safety and tolerability will be assessed using the following primary variables:

- Adverse events (AEs) reported spontaneously by the subject and/or caregiver (including parent/legal guardian) or observed by the investigator
- Subject withdrawals due to AEs

#### **2.2.2.2 Other safety variables**

The other safety variables include:

- Changes in hematology, clinical chemistry, and endocrinology parameters
- Changes in 12-lead electrocardiograms (ECGs)
- Changes in vital sign measurements (ie, blood pressure [BP] and pulse rate)
- Physical and neurological examination findings
- Changes in body weight, height, and calculated body mass index
- Behavioral assessments (Achenbach Child Behavior Checklist/1½-5 [CBCL/1½-5] or CBCL/6-18)
- Cognitive function assessments (BRIEF-P/BRIEF)

### **2.2.3 Pharmacokinetic variables**

Plasma concentrations of LCM and concomitant AEDs will be obtained in order to:

- Develop a population PK model of LCM

- Investigate the effect of LCM on the steady-state plasma concentrations of concomitant AEDs
- Investigate the correlation between LCM plasma concentrations and efficacy or safety

### 2.3 Study design and conduct

This is a Phase 3, multicenter, double-blind, randomized, placebo-controlled, parallel-group study to evaluate the efficacy and safety of LCM (LCM 8mg/kg/day to 12mg/kg/day [oral solution] for subjects weighing <30kg, LCM 6mg/kg/day to 8mg/kg/day [oral solution] for subjects weighing  $\geq$ 30kg to <50kg, and LCM 300mg/day to 400mg/day [tablets] for subjects weighing  $\geq$ 50kg, or matching placebo) as adjunctive therapy in subjects with epilepsy  $\geq$ 4 years to <17 years of age with uncontrolled partial-onset seizures. Subjects weighing  $\geq$ 50kg who are unable or unwilling to swallow tablets may receive LCM oral solution. However, they are not permitted to exceed the maximum dose of LCM 400mg/day.

A total of approximately 300 subjects are planned to be randomized at approximately 155 sites. The study will be conducted in the [REDACTED] region with the possibility to expand the study to other countries and regions if deemed necessary.

Stratification of subjects by age category is planned to ensure that an appropriate number of subjects will be included in each age range. The age categories are as follows:

- At least 100 subjects  $\geq$ 4 years to <12 years of age
- At least 100 subjects  $\geq$ 12 years to <17 years of age

Subjects with uncontrolled partial-onset seizures will be enrolled into an 8-week Baseline Period. At the end of the Baseline Period (Visit 2), eligible subjects will be randomized in a double-blind manner to 1 of 2 parallel treatment arms: LCM or placebo in a 1:1 ratio. At the end of Visit 2, subjects should take the first dose of study medication while in the clinic. At each subsequent clinic visit, subjects should take study medication (and any concomitant AEDs) at the regular times. Study medication will be administered orally bid at approximately 12-hour intervals in the morning and in the evening.

Eligible subjects will enter a 6-week Titration Period (with study medication dosing flexibility allowed based on tolerability) to achieve the target Maintenance Period dose (LCM 8mg/kg/day to 12mg/kg/day for subjects weighing <30kg, LCM 6mg/kg/day to 8mg/kg/day for subjects weighing  $\geq$ 30kg to <50kg, and LCM 300mg/day to 400mg/day for subjects weighing  $\geq$ 50kg, or matching placebo). Subjects must achieve the minimum target dose for their body weight category for the final 3 days of the Titration Period to be eligible for entry into the Maintenance Period. If it becomes apparent that a subject will not be able to reach the minimum target dose, then the subject should be withdrawn from the study and enter the Taper Period.

Subjects who achieved at least the minimum target study medication (LCM or matching placebo) dose for the final 3 days of the Titration Period will enter a 10-week Maintenance Period on the study medication dose achieved on the final day of the Titration Period. Lacosamide dose (or matching placebo) will remain stable throughout the Maintenance Period. Subjects who complete the Maintenance Period and plan to participate in the open-label extension study (EP0034) will enter the blinded Transition Period. Subjects who require a change in dose during the

Maintenance Period will be withdrawn and enter the blinded Taper Period. Subjects who choose not to participate in EP0034 will also enter the Taper Period.

Subjects who complete the Maintenance Period and plan to participate in the open-label extension study (EP0034) will enter a 4-week blinded Transition Period. Subjects randomized to LCM will maintain their Maintenance Period dose during the Transition Period. Subjects randomized to placebo will transition to LCM in a double-blind fashion in accordance with the schedule provided in Table 7-4 of the protocol.

The blinded Taper Period (2 to 4 weeks, depending on dose level achieved) is for subjects who will not be entering the open-label extension study (EP0034) for any of the following reasons:

- Subject does not complete the Titration Period, the Maintenance Period, or the Transition Period
- Subject does not choose to enroll in the open-label extension study (EP0034) after completing the Maintenance Period or the Transition Period

Taper of LCM may not be required for some subjects who discontinue study medication prematurely, depending on the treatment option selected by the investigator in consultation with the subject and/or parent/legal representative.

The dosing of study medication for the Taper Period is provided in Table 7-5 of the protocol .

There will be a 30-day Safety Follow-Up Period for subjects not entering the open-label extension study (EP0034).

Unscheduled visits can be conducted at the discretion of the investigator.

Each subject's total duration of study medication administration is up to 24 weeks. The total study duration can be up to 36 weeks, including the 30-day safety Follow-Up Period.

Detailed tabular schedules of study procedures and a study schematic diagram are included in sections 5.2 and 5.3 of the protocol, respectively.

## 2.4 Determination of sample size

Assuming an effect size of 0.342, in which the effect size was calculated using a placebo-subtracted difference of -0.249 and a common SD of 0.73 on the log-transformed data, the difference of -0.249 on the log-transformed data is equivalent to approximately 22% reduction over placebo after exponentiation. With this effect size, power of 80%, and a 2-sided test at the 5% level of significance, a sample of 135 subjects in each treatment arm will be needed.

Assuming a responder rate of 22% and 40% for the placebo and LCM groups, respectively, a 2-sided continuity corrected Chi-square test at a significance level of 5% will provide approximately 87% power with 135 subjects in the placebo group and 135 subjects in the LCM group.

To account for an anticipated subject dropout rate of approximately 14%, the planned number of subjects to enroll is 154 subjects per treatment arm.

### 2.4.1 Blinded sample size re-estimation procedure

After 50% of subjects have been randomized, completed the study (including those who discontinued), and have Baseline and post-Baseline seizure data available for analysis, a sample size re-estimation procedure will be performed in 2 consecutive stages of adjustment:

- Stage 1: Initial sample size re-estimation. An initial sample size re-estimation with equal allocation in each treatment arm will be performed using the related residual variance combined with Guenther adjustment (Friede and Kieser, 2011) to give a revised sample size to be adjusted in Stage 2 and Stage 3. This value will not be adjusted by more than 10% above the current estimate of 135 subjects per treatment arm (ie, the initial sample size re-estimate will not be adjusted above 149 subjects per treatment arm).
- Stage 2: Adjustment for drop-out rate. The overall study drop-out rate will be determined. The current SP0969 protocol plans for a 14% overall study drop-out rate for use in determination of sample size. If the actual overall study drop-out rate is >14%, UCB plans to adjust the sample size from Stage 1 accordingly, using an overall study drop-out rate up to a maximum of 24% (ie, the original estimated overall study drop-out rate can be increased by a maximum of 10%).

## 3 DATA ANALYSIS CONSIDERATIONS

### 3.1 General presentation of summaries and analyses

Statistical analysis and generation of tables, figures, subject data listings, and statistical output will be performed using SAS Version 9.3. All tables and listings will use Courier New font size 9.

Descriptive statistics will be displayed to provide an overview of the study results. For categorical parameters, the number and percentage of subjects in each category will be presented. The denominator for percentages will be based on the number of subjects appropriate for the purpose of analysis. Unless otherwise noted, all percentages will be displayed to 1 decimal place. No percentage will be displayed for zero counts, and no decimal will be presented when the percentage is 100%. For continuous parameters, descriptive statistics will include number of subjects (n), mean, standard deviation (SD), median, minimum, and maximum.

Decimal places for descriptive statistics will always apply the following rules:

- “n” will be an integer.
- Mean, SD, and median will use 1 additional decimal place compared to the original data.
- Coefficient of variance (CV[%]) will be presented with 1 decimal place.
- Minimum and maximum will have the same number of decimal places as the original value.

Statistical tests of efficacy variables will be presented as 2-sided p-values rounded to 4 decimal places. P-values less than 0.0001 will be presented as “<0.0001” and p-values greater than 0.9999 will be presented as “>0.9999.” Statistical comparison will be performed at the 0.0500 level of significance.

A complete set of data listings containing all documented data and all calculated data (eg, change from Baseline) will be generated, and will be sorted by site, subject number and visit (where applicable).

## **3.2 General study level definitions**

### **3.2.1 Analysis time points**

#### **3.2.1.1 Last dose of study medication**

Unless otherwise noted, all references to the last dose of study medication in this SAP refer to the last dose of study medication taken across all study periods (ie, the last dose of study medication across the Titration, Maintenance, Transition, and Taper Periods). The last dose of study medication during the Treatment Period will be defined as the last dose during the Titration and Maintenance Periods.

#### **3.2.1.2 Relative day**

Relative day will be calculated as the current date minus the date of first dose of study medication plus 1 for days on or after the day of first dose of study medication and prior to or on the day of last study medication dose (eg, the day of first dose will be Day 1.) Relative day will be calculated as the current date minus the date of first dose of study medication for days prior to the first dose of study medication (the day prior to first dose will be Day -1). For days after the last dose of study medication, relative day will be calculated as the current date minus the date of last dose of study medication including a “+” to denote post-treatment days (eg, the day after the last dose will be Day +1). Relative day will not be calculated for partial or missing dates.

### **3.2.2 Study periods**

The study consists of the following six periods: Baseline Period, Titration Period, Maintenance Period, Transition Period, Taper Period, and Safety Follow-Up Period. Additionally for analysis purposes, the Treatment Period includes Titration and Maintenance Periods. Each period is defined in turn as follows for the classification by study period:

#### Baseline Period

On or after the date of Visit 1 (entry to study) and prior to the date of first dose of study medication.

#### Titration Period

On or after the date of first dose of study medication and prior to or on the end date of the Titration Period (Visit 5) for subjects who complete the Titration Period, or on or after the date of first dose of study medication and prior to or on the date of the Early Termination Visit (ETV) for subjects who discontinue during the Titration Period. If a subject does not have a Visit 5/ETV, then either the date of the last scheduled or unscheduled visit during the Titration Period or the date of last known dose of study medication during the Titration Period, whichever is later, will define the end date of the Titration Period.

#### Maintenance Period

The day after the end of the Titration Period (Visit 5) and prior to or on the end date of the Maintenance Period (Visit 8) for subjects who complete the Maintenance Period, or the day after the end of the Titration Period (Visit 5) and prior to or on the date of the ETV for subjects who

discontinue during the Maintenance Period. If a subject does not have a Visit 8/ETV, then either the date of the last scheduled or unscheduled visit during the Maintenance Period or the date of last known dose of study medication during the Maintenance Period, whichever is later, will define the end date of the Maintenance Period.

#### Treatment Period

On or after the date of first dose of study medication and prior to or on the end date of the Treatment Period (Visit 8) for subjects who complete the Treatment Period, or on or after the date of first dose of study medication and prior to or on the date of the ETV for subjects who discontinue during the Treatment Period. If a subject does not have a Visit 8/ETV, then either the date of the last scheduled or unscheduled visit during the Treatment Period or the date of last known dose of study medication during the Treatment Period, whichever is later, will define the end date of the Treatment Period.

#### Transition Period

For those subjects who complete the Maintenance Period and plan to participate in the open-label extension study (EP0034), the Transition Period is defined as the date after the last dose of study medication in the Maintenance Period and prior to enrollment into EP0034.

#### Taper Period

For those subjects who discontinue study medication or for those subjects who complete the Maintenance Period but choose not to enter EP0034, the Taper Period is defined as the date after the last dose of study medication in the Titration, Maintenance or Transition Periods, as appropriate, and the date of last dose of study medication.

#### Safety Follow-Up Period

There will be a 30-day Safety Follow-Up Period for subjects not entering EP0034. The Safety Follow-Up Period is defined as the date after the last dose of study medication in SP0969 and continues until the date of last telephone contact and/or 30 days after the last dose of study medication, whichever is later.

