8.8 Early Termination Visit

Subjects who withdraw from the study prematurely for any reason, including AEs, must complete an Early Termination Visit. At the time of withdrawal from the study, investigators should discuss treatment options with the subject and/or their parent/legal guardian to best manage the subject's epilepsy. Taper of LCM may not be required for some subjects who discontinue study medication prematurely, depending on the treatment option selected by the investigator in consultation with the subject and/or parent/legal guardian. These subjects should complete the Early Termination Visit and then complete the 30-day Safety Follow-Up Period.

The following assessments should be completed at the Early Termination Visit and prior to subjects entering the blinded Taper Period (2 to 4 weeks).

- Concomitant medications
- Concomitant AEDs
- Changes in VNS settings
- Physical examination (complete)
- Tanner Stage assessment
- Vital signs (BP and pulse rate, including orthostatic assessments)
- Body weight assessment
- Height assessment
- Head circumference
- Neurological examination (complete)
- 12-lead ECG (2 interpretable recordings to be performed prior to any blood draws and vital signs assessment and, if possible, with the subject in the supine position for approximately 5 minutes preceding the recordings and during the recordings)
- Blood sample for clinical chemistry and hematology
- Blood sample for endocrinology
- Urine sample for urinalysis (for subjects ≥ 5 years of age)
- Serum pregnancy test (for females of childbearing potential)
- Blood sample for measurement of concomitant AED plasma concentrations
- Blood sample for measurement of LCM plasma concentration
- C-SSRS (for subjects ≥ 6 years of age)
- Clinical Global Impression of Change
- Caregiver's Global Impression of Change
- Achenbach CBCL (same version used at Visit 2)
- BRIEF-P/BRIEF score (version consistent with that used at Visit 2)
- PedsQL score (version consistent with that used at Visit 2)
- Contact IXRS
- Dispense study medication for the Taper Period (2 to 4 weeks)
- Study medication return
- Reminder to complete subject diary on a daily basis
- AE reporting
- Health care resource use

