## 10.2 Adverse events

AEs will be tabulated by MedDRA SOC and MedDRA PT. The number and percentage of subjects experiencing each event at least once will be summarized. All summaries will be sorted alphabetically by SOC and by frequency of events within PTs, starting with the most frequent event overall.

AEs will be classified as pre-treatment, treatment-emergent, or post-treatment. Pre-treatment AEs are defined as AEs which had an onset date prior to the first study medication administration. Treatment-emergent adverse events (TEAE) are defined as those events which start on or after the date of first study medication administration and within 30 days following the date of last study medication administration, or whose severity worsens within this time frame. Post-treatment AEs are defined as AEs which had an onset date after 30 days after the last study medication administration.

All AEs reported during the study including pre-treatment and post-treatment AEs will be provided in a subject data listing.

An overall summary of AEs will provide the overall summary of TEAEs and the numbers and percentages of subjects with at least 1 TEAE, with a serious TEAE, with a TEAE that led to permanent withdrawal of study medication, with a drug-related TEAE, with a severe TEAE, and with a drug-related serious TEAE. The number and percentage of subject discontinuations due to TEAEs, and the number and percentage of subjects with AEs leading to death (if applicable), will also be summarized. This overall summary will be repeated by treatment group and age group, and by treatment group and weight group using the levels defined in section 4.8.

The following summaries of AEs will be provided for each treatment group by MedDRA primary SOC and PT:

- Incidence of TEAEs
- Incidence of serious TEAEs
- Incidence of TEAEs leading to discontinuation of study medication

All three of these summaries will then be repeated by treatment group and age group, using the levels defined in section 4.8. In addition, all three of these summaries will be repeated including the site and subject number of all those subjects experiencing each TEAE and will be presented by treatment group.

The incidence of TEAEs during the Titration, Maintenance, Transition, Taper, and Safety Follow-Up Periods, separately, will also be presented for each treatment group by MedDRA primary SOC and PT.

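### SAP 3.2.2 lets Titration or Maintenance overlap with Safety Follow-Up or Taper when a discontinuing subject's last dose precedes the Early Termination Visit, so an adverse event can fall in two columns of the by-period TEAE table

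*SAP*

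**What the plan says.** SAP 3.2.2 (Study periods) closes the on-treatment periods by visit. For a subject who leaves during Titration, that period runs "prior to or on the date of the Early Termination Visit (ETV) for subjects who discontinue during the Titration Period". For one who leaves during Maintenance, the definition reads "the day after the end of the Titration Period (Visit 5) and prior to or on the date of the ETV for subjects who", meaning those who stop in that period. If there is no Visit 8 or ETV, the last visit or the last known dose in the period, "whichever is later, will define the end date of the Maintenance Period".

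The same section opens the later periods by dose. Taper begins the day after the last Titration, Maintenance or Transition dose. For the period after that, "The Safety Follow-Up Period is defined as the date after the last dose of study medication in SP0969". SAP 3.2.1.1 fixes the default meaning of last dose as "the last dose of study medication across the Titration, Maintenance, Transition, and Taper Periods", so any taper doses push the start of Safety Follow-Up later.

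The periods feed a table in SAP 10.2: "The incidence of TEAEs during the Titration, Maintenance, Transition, Taper, and Safety Follow-Up Periods, separately, will also be presented". SAP 6.4 also assigns medications to these periods by start date.

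Protocol 8.8 describes subjects who stop without taper: "These subjects should complete the Early Termination Visit and then complete the 30-day Safety Follow-Up Period". The protocol therefore places the ETV before Safety Follow-Up, whereas the SAP starts Safety Follow-Up from the dose.

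**The concern.** A set of study periods used to sort events should put each day in one period. Here one boundary is set by a visit and the next by a dose, and the two agree only when the last dose falls on the ETV date.

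The protocol foresees cases where it does not. Protocol 6.3 and 11.7 require study medication to be stopped immediately for specified liver-test results. Protocol 11.1.6 lists immediate stopping as one of two options when a subject becomes pregnant, together with a return for an ETV. In either case days can pass between the last dose and the visit.

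What is at stake is a descriptive safety table. Events just after stopping are ones that a by-period display should place correctly. As written, the programmer must either count such an event under two periods or invent a tie-break. Under the first course, and possibly the second, an off-drug event is shown as a Titration or Maintenance event.

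**Working it through.** The documents give no figure for the overlap, so there is none to reproduce. The check applies the definitions as written to dates.

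**Rules used**
- Maintenance days for a discontinuer: Visit 5 + 1 to ETV (SAP 3.2.2).
- Safety Follow-Up days: last dose overall + 1 onward, for at least 30 days (SAP 3.2.2 with 3.2.1.1).
- Taper days: last Titration, Maintenance or Transition dose + 1 to last dose overall (SAP 3.2.2).

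**Case A: permanent stop without taper.** The overlap of Maintenance with Safety Follow-Up runs from last dose + 1 to the ETV, so its length is ETV day minus last-dose day. I assume Visit 5 on Day 42, so Maintenance starts on Day 43 and has (ETV day − 42) days. The last-dose and ETV days are also assumed.

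| Last dose | ETV | Maintenance days | Days in both periods | Share |
|---|---|---|---|---|
| Day 60 | Day 60 | 18 | 0 | 0% |
| Day 60 | Day 62 | 20 | 2 | 10% |
| Day 60 | Day 67 | 25 | 7 | 28% |
| Day 60 | Day 74 | 32 | 14 | 44% |
| Day 100 | Day 107 | 65 | 7 | 11% |
| Day 44 | Day 51 | 9 | 7 | 78% |

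The same arithmetic holds for Titration, with the first-dose date in place of Visit 5 + 1.

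**Case B: pause before the ETV, then taper.** Safety Follow-Up now starts after the last taper dose and does not meet Maintenance. But Taper starts the day after the last Maintenance dose. With that dose on Day 60, an ETV on Day 67 and taper doses afterwards, Days 61 to 67 (67 − 60 = 7 days) lie in both Maintenance and Taper.

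**Case C: last dose on the ETV date.** There is no overlap.

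**Search for a tie-break.** SAP 3.2.2, 4.2 and 10.2 contain no rule on which period prevails.

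**Ceiling on the number affected.** Planned enrolment is 2 × 154 = 308 and planned dropout about 14% (SAP 2.4): 0.14 × 308 ≈ 43, or 0.14 × 154 ≈ 22 per arm. These are all planned dropouts. Only those whose last Titration or Maintenance dose precedes the period's end date count, and the documents do not give that share.

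**Check of the remedy.** If Maintenance ends at the earlier of the ETV and the last dose in that period, it ends on Day 60 in every Day 60 row, on Day 100 and Day 44 in the other two, and on Day 60 in Case B. The overlap is then 0 days throughout.

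**The case against.** The strongest reply is that very little turns on this. Taper is the default for discontinuers, and Protocol 8.8 places the ETV before Taper, with taper medication dispensed there. Most subjects should therefore be dosing up to the visit. The protocol's instruction to attend as soon as possible after an AE that leads to withdrawal does not say that drug stops first, and the no-taper route does not say so either. TEAE status, and the overall, serious and discontinuation tables, depend on first dose to 30 days after last dose, not on these periods. All of that stands and limits the point to one by-period table and the period labels on listed medications. It does not supply the missing rule.

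Four stronger readings are tempting and are not supported.

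- **That every dropout is affected.** The Safety Follow-Up overlap needs a permanent stop without taper before the ETV, and the Taper overlap needs a pause before it. The figure of 43 is a ceiling.
- **That health care use and concomitant medication summaries are double counted.** SAP 8.3.4 to 8.3.6 plan procedure, consultation and hospital/ER summaries only for Baseline and the Treatment Period. SAP 6.4.5 and 6.4.8 define concomitant use by at least one shared day with study medication.
- **That the SAP plans to count events twice.** It does not say so. Double counting follows from two definitions and the lack of a tie-break.
- **That off-drug diary days make the primary analysis wrong.** The ETV cut-off for seizure data is explicit in 3.2.2, is repeated in the observed-case analysis (SAP 8.1.4), and was kept when SAP Amendment 2 revised the Maintenance definition. Cutting at the last dose would carry a short on-drug stretch over 10 weeks and could favour lacosamide. An example can be built in which a responder becomes a non-responder: take a baseline rate of 10 per 28 days, 4 on drug, 10 off drug, and a share s of the window off drug. The frequency is 4 + 6s, which exceeds 5 only when s is above one sixth. With 7 of 17 days off drug it is 6.5; with 2 of 12 it is exactly 5.0, still a 50% reduction. Rates and gap are all assumed. This is a choice of what to estimate, not an inconsistency.

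**Conclusion.** The point holds for adverse-event classification. Read as written, SAP 3.2.2 places the days from last dose plus one to the ETV in two periods: Titration or Maintenance with Safety Follow-Up if there is no taper, and with Taper if dosing resumes for taper. A TEAE starting on those days qualifies for two columns of the SAP 10.2 by-period table, one of which describes the subject as in Titration or Maintenance when off drug.

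Per subject, the size is the gap between last dose and ETV. Across the study it cannot be stated: it is some part of the planned 14% dropouts, and the gap lengths above are assumptions. The conclusion also assumes that TEAEs are assigned to periods by onset date, which SAP 10.2 does not spell out. The effect is confined to a descriptive table and medication period labels. It is worth correcting because the correction is nearly free, not because a main conclusion depends on it.

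**What to change.** Add to SAP 3.2.2, for discontinuing subjects and for assigning adverse events and listed medications to periods only: Titration and Maintenance end at the earlier of the ETV (or the substitute end date where no ETV was held) and the last dose taken in that period. Later days then belong only to Taper or Safety Follow-Up. The last dose should be identified from the period as now defined, so that the rule is not circular.

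Keep the ETV end date for Last Visit (SAP 3.2.4), for markedly abnormal laboratory and vital-sign values (SAP 10.3 and 10.4.1), which need the Treatment Period to include the ETV, and for seizure frequency.

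Starting the next period the day after the ETV would also remove the overlap, but it would leave off-drug events labelled as Titration or Maintenance, so it is the weaker remedy.

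The cost is a sentence or two in the SAP and one programming condition on dates already collected. The small downside is a second period end date, used only for event and medication classification, which the table footnotes should state.
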